### 3.2 Study Sites

The study will enrol up to 20 Canadian sites.

### 3.3 Sample Size

The study will include up to **200** patients. No formal sample size calculation has been carried out. The planned number of patients to be enrolled in the study should be adequate for the exploratory purposes and allow a conclusion to be drawn regarding the use of Akynzeo® in the Canadian medical environment.

### 3.4 Primary Endpoint

The primary endpoint is the FLIE total score for cycle 1.

### 3.5 Secondary Endpoints

The secondary endpoints are:

- FLIE total score cycles 2-4
- FLIE Nausea domain total score all cycles
- FLIE Vomiting domain total score all cycles
- Complete response-no emesis, no rescue medication during the acute, delayed and overall phase all cycles
- No significant nausea during the acute, delayed and overall phase for all cycles
- Time to failure defined as time to first emetic episode or time to rescue medication use for all cycles
- Use of rescue medication all cycles
- To descriptively assess the patient diary at screening and over time

The response to Akynzeo® and the necessity for use of a rescue medication will be recorded to evaluate effectiveness. Any medicinal products used as rescue medication will be recorded in the patient diary.

### 3.6 Exploratory Endpoints

- To descriptively assess HEOR parameters (ER visits, hospitalizations)
- To descriptively assess the WPAI-NV

### 3.7 Safety Assessment

Safety will be evaluated by the incidence and type of adverse events (AEs), serious adverse events (SAEs) and AEs leading to discontinuation of treatment in all patients.

## 4 SUBJECT SELECTION AND WITHDRAWAL

Protocol waivers will not be provided by the sponsor. All subjects included in this study must meet all of the inclusion criteria and none of the exclusion criteria. Deviations from the protocol will be noted as such and will be addressed by the sponsor as appropriate.

### 4.1 Inclusion Criteria

Subjects must satisfy the following criteria to be enrolled in the study:

1. Patient scheduled to receive a highly emetogenic chemotherapy (HEC).
2. Patient scheduled to receive antiemetic prevention with Akynzeo® according to the approved Canadian Product Monograph as deemed medically necessary by the participating physician independently from this study.
3. Age  $\geq$  18 years.
4. Women of childbearing potential must use effective contraception during therapy and up to one month after treatment with Akynzeo®.
5. Patient (and/or patient's authorized legal representative) should understand the nature of the study and provide written informed consent prior to or at the screening visit.
6. Patient is able and willing to comply with the study protocol for the entire length of the study and will follow all study requirements, procedures and complete all visits as required.
7. Patient is participating in another clinical trial where antiemetic treatment is not pre-specified by the study protocol.

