### 4.2 Exclusion Criteria

Potential subjects who meet any of the following criteria will be excluded from participation in the study:

1. Women of child bearing potential who are pregnant, planning on becoming pregnant or breast feeding.
2. Hypersensitivity to active substances, excipients or other ingredients of Akynzeo®.
3. Concomitant use of pimozide, terfenadine, astemizole, or cisapride.
4. Patient currently enrolled in another clinical trial where antiemetic treatment is pre-specified by the study protocol.

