### 7.3 Efficacy and Safety Analysis

This is a two year (approximately), multi-centre, prospective, observational study designed to collect clinical data on the real-world use of Akynzeo® in Canada. All analyses will be descriptive in nature.

Before beginning data analysis, plausibility checks will be performed. Implausible or ambiguous data will be excluded from analysis.

Prior to database lock, a statistical analysis plan (SAP) defining all details of analysis will be prepared. A table mock-up (TMU) document which will illustrate the details of presentation and analysis for data collected in this study will accompany this document.

The Intent-To-Treat (ITT) population includes all patients who were entered into the study web-based application and have a date of signed informed consent available. This population will be used to provide descriptives for patients enrolled by centre, patient disposition and reasons for screen failure.

The modified Intent-To-Treat (mITT) population includes all patients who were included in the ITT population and fulfilled all entry criteria and received at least one dose of the study treatment (Akynzeo®). Missing questionnaires/assessments will not be imputed. The mITT population will be used for the analysis of the primary, secondary and exploratory endpoints not including health resource utilisation (ER visits, hospitalizations). This population will also be used for demographic, medical history and concomitant medication tables.

The Safety population includes all patients who received at least one dose of the study treatment (Akynzeo®). This population will be used for all safety analyses and health resource utilisation (ER visits, hospitalizations) tables.

Continuous variables will be summarized descriptively by number of observations, number of missing observations, mean, standard deviation, median, 1st quartile, 3rd quartile, minimum and maximum. Categorical variables will be summarized descriptively as frequency counts and percentages.

A number of p-values may be presented in the reported tables for exploratory purposes. Statistical testing will be performed at the two-sided 0.05 significance level unless otherwise specified. P-values will not be adjusted for multiple comparisons.

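### Inclusion criterion 7 words a permission as a requirement: read literally, every subject must be in another clinical trial, and anyone who is not falls out of the primary analysis set

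*Combined protocol and SAP*

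**What the plan says.** The inclusion list in Section 4.1 opens by making every item a condition of enrolment. Item 7 reads "Patient is participating in another clinical trial where antiemetic treatment is not pre-specified by the study protocol". It contains no conditional word, and the synopsis repeats it in the same words.

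Section 4 makes the list binding: "All subjects included in this study must meet all of the inclusion criteria and none of the exclusion criteria", and "Protocol waivers will not be provided by the sponsor". The matching exclusion (Section 4.2, item 4) is "Patient currently enrolled in another clinical trial where antiemetic treatment is pre-specified by the study protocol".

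Section 7.3 carries the eligibility list into the analysis sets. mITT takes ITT patients who "fulfilled all entry criteria and received at least one dose of the study treatment (Akynzeo". On its use: "The mITT population will be used for the analysis of the primary, secondary and exploratory endpoints not including health resource utilisation (ER visits, hospitalizations"; and further, "This population will also be used for demographic, medical history and concomitant medication tables". The Safety population carries no eligibility condition: "The Safety population includes all patients who received at least one dose of the study treatment (Akynzeo".

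The synopsis indication and Sections 1.5 and 7.1 also restrict the population to chemotherapy lasting no more than 2 days. No numbered inclusion or exclusion criterion states that limit.

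**The concern.** Item 7 looks like one half of an allowed/not-allowed pair with exclusion 4, placed by mistake among the mandatory conditions. As it stands, concurrent enrolment in another trial is a requirement. That sits badly with Section 1.2, which wants routine practice, and with Section 4.3, which recruits through charts, referral, advertising and outreach.

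This would be loose drafting and no more if eligibility stopped at the clinic door. It does not, because membership of mITT depends on having met every entry criterion. Who counts in the primary analysis therefore depends on how someone reads one sentence. Two things are at stake:

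- **Who enters.** Sites that follow the text would turn away patients who are in no other trial.
- **Who is analysed.** If sites disregard the text, the effectiveness and baseline tables (mITT) and the safety and resource-use tables (Safety) would, under the written definitions, describe different patients.

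The 2-day limit raises a related problem in the opposite direction. A patient outside the stated population could pass every listed criterion and enter mITT.

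**Working it through.** The plan gives no figure to reproduce on this point. Sections 3.3 and 7.2 set up to 200 patients without a formal calculation, and no SD, effect size or precision target is stated. The check is mainly one of wording.

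**Step 1: Is item 7 conditional?** No. Item 4 of the same list limits itself to women of childbearing potential, so the protocol does confine a criterion to a subgroup when it intends to. Item 7 has no such limit.

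**Step 2: Does another rule relax it?** Section 4 says the reverse: all inclusion criteria must be met and there are no waivers. Exclusion 4 bars only trials that pre-specify antiemetics, which suggests the intent but does not make a patient in no other trial eligible under Section 4.1. No sentence in the available text does that.

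**Step 3: Which outputs are affected?**

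| Set (Section 7.3) | Must meet entry criteria? | Used for |
|---|---|---|
| ITT | No | Enrolment by centre, disposition, screen-failure reasons |
| mITT | Yes | Primary and secondary endpoints, WPAI-NV, demographics, medical history, concomitant medication |
| Safety | No | Safety, ER visits, hospitalizations |

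**Step 4: Consequences for 200 enrolled.** Let s be the share of enrolled patients who are also in another trial of the permitted kind. The documents do not give s.

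1. Sites apply the text: all 200 are participants in other trials, and mITT loses nobody on this ground. The harm is to recruitment and representativeness.
2. Sites ignore the text and the mITT rule is applied as written: mITT = 200 × s, while Safety stays at 200.
3. Everyone reads it as a permission: no effect.

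**Step 5: Illustration for case 2 only.** The 95% half-width for a mean, in SD units, is t(0.975, n − 1)/√n. The values of s are assumptions.

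| s (assumed) | n = 200 × s | Half-width (SD) |
|---|---|---|
| 5% | 10 | 0.72 |
| 10% | 20 | 0.47 |
| 20% | 40 | 0.32 |
| 50% | 100 | 0.20 |
| criterion removes nobody | 200 | 0.14 |

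With normal quantiles in place of t, the first four rows become 0.62, 0.44, 0.31 and 0.20, and the last is unchanged. At s = 0 the mITT set would be empty. All rows suppose that every enrolled patient is dosed, otherwise eligible and returns the cycle 1 FLIE. Section 7.3 does not impute missing questionnaires, so real numbers would be lower.

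**The case against.** The best defence is that nobody would read item 7 literally. Exclusion 4 mirrors it, Sections 1.5 and 7.1 describe the population without mentioning another trial, and Section 1.2 bases inclusion on the physician's free choice of Akynzeo. Case 2 also needs two opposite readings in one study: sites treating the item as a permission and the analysis then treating it as a requirement. The SAP promised in Section 7.3 before database lock could prevent that. The half-widths rest on assumed shares, the analyses are descriptive, and no precision target is missed.

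Most of this is fair, and it limits how serious the point is. The permissive intent is very likely, and the half-widths show direction only. Even in case 1, a trial that leaves antiemetics open still leaves that choice to the physician, so the loss is in which patients are represented and not in how antiemetics are chosen.

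What the defence does not do is cure the text. Clear intent is a reason to correct the line, since exclusion 4 already does the work and item 7 adds only ambiguity. A later SAP can settle mITT membership, but it cannot recover patients turned away at any of up to 20 sites. The consent form and any eligibility page of the case report form were not available here; they might show how sites were instructed, but would not change Section 4.1.

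On the 2-day limit, inclusion 2 refers to the Product Monograph, which is not among the documents. Whether that limits duration indirectly cannot be settled, so that part supports only a request for reconciliation.

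**Conclusion.** The concern holds and should be fixed. As written, Sections 4, 4.1 and 7.3 together either restrict enrolment to participants in other trials or remove everyone else from the set used for the primary endpoint. The reading is certain as a matter of text; that the item was meant as a permission is a strong inference.

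The numerical effect is not determined by the documents. It runs from none, if all parties read the item permissively, to an mITT of 200 × s if the written rule is applied to patients enrolled without regard to item 7. Safety, ER-visit and hospitalization tables do not lose patients through the mITT rule, although under case 1 they too would cover only trial participants.

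**What to change.** Delete item 7 from Section 4.1 and from the synopsis and rely on exclusion 4. Alternatively, reword it as a conditional note: taking part in another trial is allowed provided that trial does not pre-specify antiemetic treatment. Add one sentence to the SAP stating that not being in another trial does not count as a failed entry criterion for mITT.

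Separately, reconcile the 2-day population statement in the synopsis and Sections 1.5 and 7.1 with the eligibility lists. Which rule is right is for the sponsor to decide.

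The cost of the item 7 change is one line in two places and one SAP sentence. It needs no additional patients, visits or procedures. It is best made before sites screen, because the SAP cannot undo exclusions already made.

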### 4.2 Exclusion Criteria

Potential subjects who meet any of the following criteria will be excluded from participation in the study:

1. Women of child bearing potential who are pregnant, planning on becoming pregnant or breast feeding.
2. Hypersensitivity to active substances, excipients or other ingredients of Akynzeo®.
3. Concomitant use of pimozide, terfenadine, astemizole, or cisapride.
4. Patient currently enrolled in another clinical trial where antiemetic treatment is pre-specified by the study protocol.

### 4.3 Subject Recruitment and Pre-Screening

To recruit subjects for this study, any of the following recruitment methods will be acceptable following approval by the Sponsor: review of medical charts from the investigator or sub-investigator's clinical practices, referral from other physicians, any type of media advertisement and community outreach/engagement. All screened subjects will be recorded on a screening/enrolment log.

Any information to be disseminated to potential subjects (handouts, brochures, subject cards etc.) and any advertisements intended to be used for this study (printed ads, posters, flyers, spots etc.) must be approved by the site's REB prior to any use.

### 4.4 Subject Withdrawal Criteria

Subjects may voluntarily withdraw from the study at any time. If a subject exits the study early all final assessments required at the Final visit should be performed and the study completion/early termination form outlining the reason for withdrawal should be completed. No data will be collected after the early termination visit date. Subjects who withdraw from the study early will not be replaced. The investigator should withdraw subjects from the study if they feel that it is in the best interest of the subject to be terminated from the study. Any administrative or other reasons for withdrawal must be documented and explained to the subject.

The Sponsor's access to the relevant subject data will survive the subject's withdrawal from the study. Withdrawal will be documented in the subject's chart and in the Case Report Form (CRF) with a detailed explanation of the reason for the withdrawal and the date of last dose of study medication.

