### **Study 3: Safety and efficacy of NEPA over repeated cycles (Gralla et al. 2014)**

Another pivotal study for clinical use of NEPA was also published by Gralla and colleagues in 2014. The multicentre, randomized, double-blind phase III study included 413 adult patients with solid tumours of different entities, which had not been previously treated with chemotherapy. Of these patients, 76 % received a non-AC-based MEC (carboplatin, oxaliplatin, doxorubicin,

cyclophosphamide, irinotecan, epirubicin, daunorubicin) and 24 % a HEC (> 90 % cisplatin, the rest dacarbazine, carmustine). Of the 412 evaluable patients in a 3:1 randomization, 308 patients were treated on Day 1 of the CTX with NEPA (300 mg netupitant + 0.5 mg palonosetron) + 12 mg dexamethasone. The remaining 104 patients were treated with 125 mg aprepitant + 0.5 mg palonosetron + 12 mg dexamethasone on day 1 of the CT followed by 80 mg aprepitant + 8 mg dexamethasone (only in case of HEC) on days 2 and 3. The primary endpoint was defined as the safety profile of NEPA administered over at least 6 CT cycles. The efficacy (complete response and prevention of severe nausea) was determined as a secondary endpoint.

Antiemetic treatment was administered in a total of 1961 CT cycles, including 1446 with NEPA and 515 with APR / PALO. 98 % of patients completed cycle 1, 75 % completed 4 cycles and 40 % of patients completed 6 cycles.

The most common treatment-related adverse events were constipation (3.6 % NEPA vs. 1 % APR / PALO) and headache (in each case 1 % for NEPA and APR / PALO), whereby the frequency did not increase with increasing number of cycles. Overall, the rate of side effects during treatment in cycle 1 was 5.2 % (n = 308) for NEPA vs. 2.9 % for APR / PALO (n = 104). These rates fell by cycle 6 to 1.6 % for NEPA (n = 124) and 0 % for APR / PALO (n = 43) on account of the decreasing number of cases. There were no concerns with regard to the cardiac safety of NEPA.

Overall, complete response rates (no vomiting, no rescue medication) were high in both study arms over all chemotherapy cycles. NEPA showed a slight, persistent numerical advantage of 2-7 % compared to APR / PALO.

In this study, Gralla et al. were able to demonstrate consistent efficacy of NEPA associated with good tolerability over multiple cycles of highly and moderately emetogenic chemotherapies [13].

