## 3 STUDY DESIGN

### 3.1 Study Overview

This two year (approximately), multi-centre, prospective, observational real-world study is designed to collect data on the use of Akynzeo® (netupitant/palonosetron) for the prevention of nausea and vomiting in oncology patients receiving highly emetogenic chemotherapy (HEC).

The visit schedule is comprised of 6 study visits (Table 1):

- Visit 1/Screening (4 weeks to 0 weeks prior to Visit 2)
- Visit 2: (Day of/but prior to 1st chemotherapy treatment administration)

- Visit 3: (Day of/but prior to 2nd chemotherapy treatment administration)
- Visit 4: (Day of/but prior to 3rd, chemotherapy treatment administration)
- Visit 5: (Day of/but prior to 4th, chemotherapy treatment administration)
- Visit 6/Final Visit

Visit 1 and 2 can be combined as determined by the investigator. Patients will report the daily occurrence and intensity of nausea and vomiting, rescue medications, adverse events (excluding nausea and vomiting) in a diary from Day 1 (chemotherapy treatment day) to Day 5/time point 0-120 hours post chemotherapy administration of each observation period.

Safety events occurring between chemotherapy cycles will be reported by the patient. Patient will have a follow up period of 28 days post the last-chemotherapy cycle.

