## 6.9 Safety Assessments

### Adverse Events

Adverse events will be reported by the subject (or, when appropriate, by a caregiver, surrogate, or the subject's legally acceptable representative) from the time of giving written informed consent through to completion of subject participation, including the follow-up period (28 days post Visit 5). Adverse events will be followed by the investigator for a length of time as determined by the sponsor. Specific details on adverse event reporting are provided in section 8 "Safety Assessment".

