### **Severe**

The symptom causes severe discomfort. The symptom can be so strong that the study subject is unable to continue participating in the study. The severity may result in termination of treatment with Akynzeo®; the symptom can be treated and/or the study subject may require inpatient treatment.

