## **9 PREGNANCY REPORTING**

If a patient becomes pregnant during the study, as soon as information about the pregnancy is received, the investigator must inform the sponsor within 24 hours (using the Pregnancy Notification Form included in Appendix 7) from the investigational staff becoming aware of it, and the subject must be withdrawn from the study without delay. Follow-up information regarding the outcome of the pregnancy and any postnatal sequelae in the infant will be required.

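### Section 4.4 stops all data collection at early termination with no safety exception, which contradicts the adverse event and pregnancy follow-up required by Sections 6.9, 8, 8.3 and 9

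*Combined protocol and SAP*

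**What the plan says.** Section 4.4 covers every early exit. It first brings the closing assessments forward: "If a subject exits the study early all final assessments required at the Final visit should be performed". It then closes the record: "No data will be collected after the early termination visit date". No day relative to the last dose is set for this visit. The section also says that the sponsor's access to a subject's data survives withdrawal, but that concerns data already held, not new collection.

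Other sections require data that can arise after that visit:

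- **Section 9 (pregnancy).** "the subject must be withdrawn from the study without delay", and in the next sentence "Follow-up information regarding the outcome of the pregnancy and any postnatal sequelae in the infant will be required". Appendix 7 supplies a Pregnancy Outcome Questionnaire that asks for gestational age, birth weight and Apgar scores.
- **Section 6.9 (AE follow-up).** "Adverse events will be followed by the investigator for a length of time as determined by the sponsor".
- **Section 8.3 (sponsor queries).** The sponsor may ask for follow-up on a reported event. The investigator then has 10 calendar days for non-serious events, and 2 business days for serious events and special situations. Withdrawal does not end this.
- **Section 8 (collection window).** AEs are collected from consent to Visit 6, described as 28 days after Visit 5 or the last dose. Section 3.1 says similarly: "Patient will have a follow up period of 28 days post the last-chemotherapy cycle".

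The window itself is not stated consistently. Section 8.1 has AEs documented in the eCRF over 5 days per observed cycle. Table 1 allows Visit 6 at any time within 28 days of cycle 4 or before the next chemotherapy cycle.

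**The concern.** The sentence in 4.4 is unconditional, and nothing elsewhere exempts safety or pregnancy data from it. A site that applies it literally would leave an AE still ongoing at exit without a later outcome. It would also miss new events between exit and 28 days after last dose, and would not obtain pregnancy outcomes. A site that follows Sections 8 and 9 instead would collect all of these. Neither site would be misreading the protocol, so the completeness of safety data could vary by site for a reason unrelated to the drug.

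The patients affected are not a random subset. The definition of a severe event in Section 8.2.1 recognises that "The symptom can be so strong that the study subject is unable to continue participating in the study". Subjects who leave because of an AE are the most likely to have an unresolved event at the exit visit. Form 6a in Appendix 6 asks whether the AE led to study discontinuation and, if so, directs the site to the Visit 6/Final Visit end-of-study form, which under 4.4 is where collection closes. Form 6b asks whether the event receded after the drug was withdrawn or reduced. That may not be answerable if nothing is recorded after exit.

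**Working it through.** The point rests on a comparison of texts. The plan gives no figure to reproduce: Sections 3.3 and 7.2 state that no formal sample size calculation was made, and no dropout rate is planned.

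**Step 1. Can each rule be met together with 4.4?**

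| Rule | What it needs after early exit | Compatible with 4.4 read literally? |
|---|---|---|
| Section 9, pregnancy outcome and infant sequelae | Data up to and after birth, although withdrawal is immediate | No, wherever the exit visit falls, because infant sequelae come after a withdrawal made without delay |
| Section 6.9, AE follow-up for a sponsor-set period | Data for as long as the sponsor decides | No, if that period runs past the exit visit |
| Section 8.3, sponsor-requested follow-up | An investigator response whenever asked | No, if the request concerns information arising after the exit visit |
| Section 8, AE collection to 28 days after Visit 5 or last dose | Data to day 28 | Only if the exit visit falls on day 28 or later |

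The pregnancy conflict is unconditional. The other three depend on timing.

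**Step 2. How much of the Section 8 window could be cut?** Let d be the day of the exit visit, counted from the last dose. The days of AE collection lost are 28 − d for d below 28, and 0 otherwise:

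- d = 0: 28 − 0 = 28 days
- d = 5: 28 − 5 = 23 days
- d = 14: 28 − 14 = 14 days
- d = 28 or later: none

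The values of d are illustrative, because 4.4 fixes none.

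**Step 3. How many patients could be affected?** The planned enrolment is up to 200 (Section 7.2). Early exit is assumed at 10%, 25% and 40%:

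- 0.10 × 200 = 20
- 0.25 × 200 = 50
- 0.40 × 200 = 80

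The middle value mirrors the only retention figures in the document, from the cited repeated-cycle phase III study in Section 1.4: "98 % of patients completed cycle 1, 75 % completed 4 cycles and 40 % of patients completed 6 cycles", so 1 − 0.75 = 0.25. That study is a weak guide here. It was randomised, 76% of its patients received moderately emetogenic non-AC chemotherapy, and the protocol does not report why patients stopped.

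**Step 4. Is the reference window itself secure?** No. Under the 5-day window in Section 8.1, an exit visit after day 5 of the last observed cycle would cut no AE collection. Under Table 1, a completer whose next cycle starts before day 28 also has fewer than 28 days.

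**The case against.** The strongest reply is that 4.4 is a general sentence, meant to end study-visit data, and that the specific safety rules prevail over it. Section 9 makes pregnancy follow-up mandatory and has its own form. Section 8.3 runs a separate pharmacovigilance channel. Form 6b has a numbered follow-up box and a lost-to-follow-up outcome, so later reports are plainly foreseen. On AEs, Section 8 ends collection at Visit 6 and 6.9 ends it at completion of participation. If 4.4 moves Visit 6 forward, the three sections arguably agree. The 28 days in 6.9 also run from Visit 5, which many early leavers never reach.

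Part of this stands. A sensible site may well continue safety follow-up, and for AE collection the conflict narrows to the last-dose wording in Section 8, together with the open-ended follow-up in 6.9 and 8.3. It does not remove the contradiction: the protocol states no order of precedence, and 4.4 speaks of data without qualification. Even where a subject revokes data authorisation, Section 12.1 asks sites to seek permission for vital status at the end of the scheduled period. Section 4.4 would bar that for an ordinary early exit.

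A reader might infer four stronger things that the documents do not support:

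- **All pregnancy outcomes are lost by rule.** Section 9 and its questionnaire require the opposite. There is a conflict, not a certain loss.
- **Completers get a full 28 days and leavers do not.** Table 1 and Section 8.1 leave this unproven, and no fixed percentage loss can be claimed without a day for the exit visit.
- **A named safety measure is lost.** Section 3.7 names the incidence and type of AEs, SAEs and AEs leading to discontinuation, not their outcomes. An AE that causes exit has already occurred and can be counted at the exit visit. Only new events after exit bear on incidence.
- **Section 8.2.1 is a further rule that 4.4 breaks.** It defines intensity and sets no follow-up.

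**Conclusion.** The contradiction holds on the text and does not depend on any assumed number. It is plainest for pregnancy, where Section 9 orders both the withdrawal and the later data. It is also clear for AEs still open at exit, through 6.9 and 8.3. For new AEs after exit it is conditional on an exit visit before day 28 and on Section 8, not Section 8.1, defining the window.

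The size of the loss is unknown. The day counts and the 20 to 80 patients are scale only, resting on assumed exit timing and assumed early exit. The number of pregnancies is not forecast and may be small. What is at stake is the completeness and between-site consistency of safety data. The primary endpoint, the FLIE total score for cycle 1, is little affected. The point should be corrected, but it does not threaten the main analysis.

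**What to change.** 1. In 4.4, limit the stop to effectiveness, diary and questionnaire data. State that AEs, SAEs, special situations and pregnancies continue to be collected and followed after early termination as Sections 6.9, 8, 8.3 and 9 already require, unless the subject withdraws consent to this. In those sections' own terms, this means AE collection to 28 days after last dose, follow-up of ongoing AEs for the sponsor-determined period, and pregnancies to outcome. No new follow-up standard is needed, and the sponsor's discretion in 6.9 can stay.
2. In Section 9, add that withdrawal from the study does not end pregnancy follow-up.
3. Reconcile the AE windows in Sections 6.9, 8 and 8.1 and the Visit 6 timing in Table 1, so that one period applies to completers and early leavers alike.
4. Check that the consent form covers contact after withdrawal. It was not available for this review, so whether it needs a change is not known.

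The cost is a few sentences of protocol text and, for each early leaver, a brief contact or chart check at about 28 days after last dose. Open events and pregnancies need further contact, but the protocol already asks for that.
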